### **Reporting Process**

The principal investigator or designee will complete and submit a FDA Form 3500A MedWatch for any event that meets the above criteria. Forms will be submitted to the CRS QA Office via email to [[contact]](mailto:[contact]).

## **18. DATA MANAGEMENT AND CONFIDENTIALITY**

### **18.1. Data Collection**

Full build studies are managed by Roswell Park CRS Data Management for analysis by Roswell Park Biostatisticians. All electronic case report form (eCRF) data are captured for these studies.

Data management activities are performed using a CTMS system that enables the collection, cleaning and viewing of clinical trial data. CRS data management designs the study-specific database and facilitates development by the Information Technology team. Once the database design is approved by the Investigator, Statistician, and Clinical Research Coordinator, the database is put into production and data entry can begin. Data can be entered and changed only by those with the rights to do so into the eCRFs.

Roswell Park Protocol No.: I 47217

## **18.2. Maintenance of Study Documents**

Essential documents will be retained per Roswell Park's policy for 6 years from the study termination date. These documents could be retained for a longer period, however, if required by the applicable local regulatory requirements or by an agreement with Roswell Park.

## **18.3. Revisions to the Protocol**

Roswell Park may make such changes to the protocol as it deems necessary for safety reasons or as may be required by the U.S. FDA or other regulatory agencies. Revisions will be submitted to the IRB/ERC for written approval before implementation.

## **18.4. Termination of the Study**

It is agreed that, for reasonable cause, either the Roswell Park Investigators or the Sponsor, may terminate this study, provided a written notice is submitted within the time period provided for in the Clinical Trial Agreement. In addition, Roswell Park may terminate the study at any time upon immediate notice if it believes termination is necessary for the safety of participants enrolled in the study.

## **18.5. Confidentiality**

All information provided to the Investigator by Roswell Park including preclinical data, protocols, CRFs, and verbal and written information, will be kept strictly confidential and confined to the clinical personnel involved in conducting this study, and no disclosure shall be made except in accordance with any right of publication granted to the Investigator. This information may be related in confidence to the IRB/ERC or other committee functioning in a similar capacity. No report or information about the study will be provided to anyone not involved in the study without consent of Roswell Park except if required by law.

Any data, specimens, forms, reports, video recordings, and other records that leave the site will be identified only by a participant identification number (Participant ID, PID) to maintain confidentiality. All records will be kept in a limited access environment. All computer entry and networking programs will be done using PIDs only. Information will not be released without written authorization of the participant.

## **19. STATISTICAL PLAN**

This is a single-arm, open-label, Phase II study of abatacept + ixazomib + dexamethasone in relapsed, multiple myeloma patients.

Summary statistics for continuous variables will include the mean, standard deviation, percentiles and range (minimum/maximum). Categorical variables will be presented as frequencies and relative frequencies; and time-to-event variables will be summarized using Kaplan-Meier methods.

The analyses will be conducted using the intent-to-treat principle, where all patients who receive or attempt to receive treatment are included. All analyses will be conducted in SAS v9.4 (Cary, NC) at a significance level of 0.1.

### **19.1. Sample Size Determination**

The sample size determination is based on the primary analysis of response rate. Prior studies have demonstrated a second-line treatment response rate of approximately 30% in this patient population (34), and we would consider a response rate for the proposed treatment combination (abatacept + ixazomib + dexamethasone) of 50-60% to be a clinically relevant improvement. Therefore, we will test the following hypotheses:

$$H_0: \pi = 0.3$$

$$H_A: \pi > 0.3$$

where  $\pi$  is the true response rate, using a one-sided Binomial exact test. If the true response rate for the proposed treatment combination is 60%, then our study design ( $n=19$ ) as a 90% chance of achieving statistical significance at  $\alpha = 0.1$ .

### **19.2. Demographics and Baseline Characteristics**

Descriptive statistics (as appropriate: n, percent, mean, median, min and max) will be used to summarize demographic and baseline characteristics.

### **19.3. Safety Cohort**

A safety lead-in cohort of  $n_1=6$  patients will be enrolled and, after each patient completes at least 1 cycle of the treatment regimen, the study will be suspended and evaluated for the safety/tolerability of the regimen. If 0 or 1 patient out of 6 has experienced a drug related toxicity requiring treatment delay or suspension, then an additional  $n_2=13$  patients are enrolled to complete the study. Otherwise, the study will be suspended and the research team will meet to discuss possible safety concerns and will decide what actions to take with respect to study continuation.

DLTs are AEs that occur within Cycle 1 and meet any of the following criteria:

1. Treatment-emergent Grade 4 or 5 AE related to ixazomib + abatacept + dex treatment (see exceptions listed in #4 below).
2. Treatment-emergent Grade 3 AE related to ixazomib + abatacept + dex (see exceptions listed in # 4 below).
3. Treatment-emergent Grade 3 seizures.
4. The following will not be considered DLTs:
  - o Non-hematologic AEs
    - Grade 3 fatigue lasting  $\leq 7$  days.
    - Grade 3 or 4 fever or febrile neutropenia for  $\leq 2$  weeks.
    - Grade 3 increase in transaminases for  $\leq 2$  weeks or Grade 4 increase in transaminases for  $\leq 7$  days.
    - Grade 3 Tumor Lysis Syndrome (TLS) for  $\leq 2$  weeks.
    - Grade 3 or 4 asymptomatic, non-hematological clinical laboratory abnormalities that return to  $\leq$  Grade 2 within 7 days or electrolyte abnormalities that resolve with replacement.
    - Grade 3 diarrhea lasting  $\leq 72$  hours that does not require total parenteral nutrition (TPN), tube feeding, or hospitalization, and the toxicity resolves to

less than grade 3 within 72 hours.

- Grade 3 nausea/vomiting lasting  $\leq$  72 hours that does not require total parenteral nutrition (TPN), tube feeding, or hospitalization, and the toxicity resolves to less than grade 3 within 72 hours.
- Grade 3 peripheral neuropathy.
- Grade 3 hyperglycemia or Grade 4 that responds to insulin therapy.
- Hematologic AEs
  - Grade 3 neutropenia of any duration or Grade 4 neutropenia lasting  $<$  14 days.
  - Grade 3 or 4 lymphopenia.
  - Grade 3 or 4 leukopenia.
  - Grade 3 or 4 thrombocytopenia without bleeding or requiring platelet transfusion.
  - Grade 3 or 4 anemia.
  - Grade 3 or 4 B-cell aplasia and hypogammaglobulinemia.

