#### **4. LOCAL AND STUDY-WIDE NUMBER OF SUBJECTS**

A maximum of 19 patients at multiple sites, including Roswell Park will be enrolled. Accrual is expected to take up to 4 years.

Patients will participate in this study for approximately 48 months from the time of enrollment.

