## 10. TREATMENT

### 10.1. Dosing and Administration

For the purpose of this study, 1 cycle = 28 days.

Treatment will be administered on an outpatient basis. All drugs will be stored, prepared and administered as detailed in their Package Inserts (see **Appendix F**). Study patients will be treated with:

**Abatacept:** A loading dose of abatacept (30 minute IV infusion) will be administered on Day 1 Cycle 1 (refer to **Table 1**), followed by 125 mg SQ on Day 2 and then 125 mg once weekly during Cycle 1 (i.e., Days 8, 15, 22) thereafter. After Cycle 1, abatacept 125 mg SQ is given on Days 1, 8, 15, 22 for all subsequent cycles.

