### **10.2. Safety Lead-in**

The first 6 patients who have completed the first cycle of the treatment regimen without experiencing dose limiting toxicity (see Section 10.3) will comprise the safety lead-in group.

Patient data for the safety lead-in portion of the study will be discussed and monitored by The Early Phase Clinical Trials committee, which meets on a regular basis per the Roswell Park Data Safety Monitoring Plan.

After a minimum of 6 patients have completed at least one cycle of the treatment regimen, the study team will meet to examine the safety/tolerability of the combination. If 0 or 1 patient out of the 6 has experienced a drug related toxicity requiring treatment delay or suspension, an additional  $n_2=13$  patients will be enrolled to complete the study. Otherwise, the study will be suspended and the research team will meet to discuss possible safety concerns and will decide what actions to take with respect to study continuation (e.g., changes in treatment regimen/ dose modifications or discontinue the study).

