## **13. RISKS TO SUBJECTS**

Although abatacept has been approved by the FDA for the treatment of rheumatoid arthritis, it has not been given to patients with multiple myeloma (other than the single patient described in Section 2.1 and Figure 2). Because abatacept has never been combined with standard chemotherapy before, there is a risk that there may be additional side effects that arise from the combination. What these side effects will be is unknown but may reflect increased side effects from the ixazomib + dexamethasone chemotherapy combination: these include tumor lysis syndrome (TLS), decreased blood counts, increased blood sugar, hypertension, diarrhea, and nerve damage. In addition, since abatacept, ixa, and dex are immunosuppressive, patients may be at additional risk for infection; however, we do not anticipate that the combination of abatacept + ixazomib + dexamethasone to generate unique side effects that are not already reported for the single agents.

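### No numeric rule pauses lead-in accrual when a second early event has already broken the 0-or-1-of-6 limit

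*Combined protocol and SAP*

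**What the plan says.** **The rule.** Section 19.3 sets a lead-in cohort of 6. The condition for enrolling 13 more is "If 0 or 1 patient out of 6 has experienced a drug related toxicity requiring treatment delay or suspension". The alternative is "Otherwise, the study will be suspended and the research team will meet to discuss possible safety concerns", and 10.2 lists what that meeting may choose: changing the regimen or doses, or discontinuing.

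**When it is applied.** Section 10.2 says "After a minimum of 6 patients have completed at least one cycle of the treatment regimen, the study team will meet". Section 19.3 says that "after each patient completes at least 1 cycle of the treatment regimen, the study will be suspended and evaluated for the safety/tolerability".

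**Who is counted.** Section 10.2 describes the lead-in group as "The first 6 patients who have completed the first cycle of the treatment regimen without experiencing dose limiting toxicity". Section 19.3 counts toxicities out of 6 patients enrolled.

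**Other provisions that bear on early events:**
- 10.2: the Early Phase committee discusses and monitors lead-in data at its regular meetings. No number triggers action.
- 10.3: a DLT takes that participant off study. Enrolment is not mentioned.
- 18.4: the centre may terminate at any time for participant safety.
- Section 20: the DSMC reviews Phase II studies twice a year and may recommend suspension.
- 19.7: no explicit interim analysis.
- 19.8: a continuous Bayesian rule, using the DLT/AE criteria, that starts once the DLT period (Cycle 1) is over.

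**The concern.** The lead-in limit is a count, and a count can be exceeded before all 6 patients have been observed. With two events among the first 2, 3, 4 or 5 enrolled patients, 0 or 1 of 6 is out of reach and the plan's own response is suspension and review. The remaining 4, 3, 2 or 1 places can still be filled, because the only scheduled decision is stated for a count out of 6.

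At stake is exposure. Section 13 says "Because abatacept has never been combined with standard chemotherapy before, there is a risk that there may be additional side effects". Patients dosed after the second event would receive the combination when the plan is already committed to stopping and looking. The protection is also uneven: 19.8 monitors later toxicity continuously and can suspend on two events in 2, 3 or 4 subjects, while Cycle 1 has no such trigger.

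**Working it through.** **1. Nearest stated figures.** The plan gives no operating characteristics for the lead-in rule. The closest are the suspension boundaries in 19.8. With a Beta(1, 2) prior and r events in n subjects, the posterior is Beta(1 + r, 2 + n − r), and suspension needs P(rate > 25%) ≥ 0.80. All 18 rows of the table reproduce to within 0.001; for example 2 of 2 gives 0.949, 2 of 3 gives 0.896 and 2 of 4 gives 0.831.

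**2. Would 19.8 close the gap?** Not for Cycle 1 events or for delays below the DLT criteria, because it starts after Cycle 1 and uses those criteria. Even if it were extended to Cycle 1, 2 of 5 gives 0.756 and 2 of 6 gives 0.679. Both fall short of 0.80, although both already break the lead-in limit.

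**3. Inputs for the size.**
- Limit: 0 or 1 of 6 (10.2, 19.3), counted over enrolled patients as in 19.3.
- True event rate p: not in the documents. Assumed range 10% to 50%. The only toxicity bound stated anywhere is 25%, in 19.8, for chronic toxicity.
- Entry: assumed one patient at a time, each outcome known before the next starts. Section 4 says "Accrual is expected to take up to 4 years" for 19 patients, so at that ceiling 48/19 ≈ 2.5 months per patient. Section 10.1 says "For the purpose of this study, 1 cycle = 28 days". The assumption is plausible, but nothing in the plan requires it.
- Events independent between patients.

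**4. Formulas.**
- P(second event occurs at patient k) = (k − 1) p² (1 − p)^(k−2), for k = 2 to 6.
- Patients spared by pausing then: 6 − k.
- P(2 or more of 6) = 1 − (1 − p)⁶ − 6p(1 − p)⁵.

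**5. Worked case, p = 0.25.**
- k = 2: 0.0625. k = 3: 2 × 0.0625 × 0.75 = 0.0938. k = 4: 3 × 0.0625 × 0.5625 = 0.1055. k = 5: 4 × 0.0625 × 0.4219 = 0.1055.
- Second event within the first 5: the sum, 0.367.
- Mean spared: 4 × 0.0625 + 3 × 0.0938 + 2 × 0.1055 + 1 × 0.1055 = 0.85.
- P(2 or more of 6) = 1 − 0.178 − 0.356 = 0.466.

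**6. Range.**

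| Assumed event rate | P(2 or more of 6) | P(second event within first 5) | Mean patients spared, all lead-ins | Mean spared when the second event is within first 5 |
|---|---|---|---|---|
| 10% | 0.114 | 0.081 | 0.17 | 2.1 |
| 20% | 0.345 | 0.263 | 0.59 | 2.2 |
| 25% | 0.466 | 0.367 | 0.85 | 2.3 |
| 30% | 0.580 | 0.472 | 1.13 | 2.4 |
| 40% | 0.767 | 0.663 | 1.70 | 2.6 |
| 50% | 0.891 | 0.812 | 2.25 | 2.8 |

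**7. Effect on go/no-go.** None. A second event at or before patient 6 is the same outcome as 2 or more of 6, so the second column holds with or without an early pause.

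**The case against.** Four arguments deserve an answer.

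*Accrual can already be stopped.* A reader might infer that the plan forces the cohort to fill. It does not. The Early Phase committee, the safety termination clause in 18.4 and the DSMC can each lead to a halt, and 17.5 has serious events reported to the sponsor within one business day. For DLT-criteria events after Cycle 1, 19.8 would suspend at a second event among 2 to 4 subjects. This stands: what is missing is a numeric rule, not the power to act.

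*Section 19.3 may already call for a pause after every patient.* Its wording can be read that way, and 10.2 does not forbid earlier evaluation. The ambiguity is real, but on either reading no decision is stated for fewer than 6 patients.

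*The go rule may not be unreachable.* If 10.2 is taken literally and patients with a DLT fall outside the 6, two DLTs do not rule out 0 or 1 of 6. The claim therefore holds on the count used in 19.3. The other reading does not help the plan, since more than 6 patients could then be dosed before review.

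*Later lead-in patients still inform the review.* A reader might infer that their data are worthless once the limit is broken. The documents do not support that. They cannot restore the go decision, but the meeting has to choose among several actions, and the qualifying event is broad: any drug-related toxicity that delays or suspends treatment, not only a DLT. This is the true cost of pausing early.

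**Conclusion.** The concern holds in limited form. Counting over 6 enrolled patients, a second event among the first 2 to 5 already commits the study to suspension and review, and no numeric rule brings that review forward. The gap is confined to Cycle 1 events and to delays below the DLT criteria.

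The size is modest unless the regimen is toxic: under one patient spared on average at event rates up to 25%, about 1.7 at 40% and 2.25 at 50%. These figures rest on assumed rates, independence and one-at-a-time entry. The study is multi-site and 4 years is a ceiling on accrual time, so entry could cluster and the saving would then be smaller. I would class this as a cheap improvement to patient safety, not a flaw in the lead-in limit.

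**What to change.** 1. Reconcile 10.2 and 19.3 on two matters: whether the 6 are enrolled patients or only those who completed Cycle 1 without a DLT, and whether evaluation follows each patient or only the sixth.
2. Add one sentence to both sections: *Lead-in accrual pauses as soon as a second enrolled lead-in patient has a qualifying event, and the review already required for more than 1 of 6 is held at that point.*

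Leave the 0-or-1-of-6 limit, the event definition and the review's options as they are.

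The cost is a short edit in two sections and a prompt count of qualifying events across sites. The downside is that, in a failed lead-in, the review may have data on fewer than 6 patients when it decides what to do next.

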### **10.3. Definition of Dose Limiting Toxicity and Discontinuation of Therapy**

DLTs are AEs that occur within Cycle 1 and meet any of the following criteria:

1. Treatment-emergent Grade 4 or 5 AE related to ixazomib + abatacept + dex treatment (see exceptions listed in #4 below).

Roswell Park Protocol No.: I 47217

2. Treatment-emergent Grade 3 AE related to ixazomib + abatacept + dex (see exceptions listed in # 4 below).
3. Treatment-emergent Grade 3 seizures.

The above AEs are considered to be DLTs if they are judged probably or definitely associated with treatment. Should they occur, individual participants will be taken off study and no further injections will be given. Toxicity will be determined using the revised NCI Common Toxicity Criteria (CTC) version 5.0 for Toxicity and Adverse Event Reporting (<http://ctep.info.nih.gov>).

4. The following **will not** be considered DLTs:

- Non-hematologic AEs
  - Grade 3 fatigue lasting  $\leq$  7 days
  - Grade 3 or 4 fever or febrile neutropenia for  $\leq$  2 weeks
  - Grade 3 increase in transaminases for  $\leq$  2 weeks or Grade 4 increase in transaminases for  $\leq$  7 days
  - Grade 3 Tumor Lysis Syndrome (TLS) for  $\leq$  2 weeks
  - Grade 3 or 4 asymptomatic, non-hematological clinical laboratory abnormalities that return to  $\leq$  Grade 2 within 7 days or electrolyte abnormalities that resolve with replacement
  - Grade 3 diarrhea lasting  $\leq$  72 hours that does not require total parenteral nutrition (TPN), tube feeding, or hospitalization, and the toxicity resolves to less than grade 3 within 72 hours
  - Grade 3 nausea/vomiting lasting  $\leq$  72 hours that does not require total parenteral nutrition (TPN), tube feeding, or hospitalization, and the toxicity resolves to less than grade 3 within 72 hours
  - Grade 3 peripheral neuropathy
  - Grade 3 hyperglycemia, or Grade 4 that responds to insulin therapy
- Hematologic AEs
  - Grade 3 neutropenia of any duration or Grade 4 neutropenia lasting  $<$  14 days
  - Grade 3 or 4 lymphopenia
  - Grade 3 or 4 leukopenia
  - Grade 3 or 4 thrombocytopenia without bleeding or requiring platelet transfusion
  - Grade 3 or 4 anemia
  - Grade 3 or 4 B-cell aplasia and hypogammaglobulinemia

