#### **17.4.6. Reporting Serious Adverse Events**

All new SAEs occurring from the date the participant signs the study consent until 30 days after the last intervention or a new treatment is started, whichever comes first, will be reported. The Roswell Park SAE Source Form is to be completed with all available information, including a brief narrative describing the SAE and any other relevant information.

SAEs occurring after the 30 day follow-up period that the investigator determines to be possibly, probably or definitely related to the study intervention should be reported.

SAEs that are unexpected and possibly, probably or definitely related must be reported as an Unanticipated Problem. Please refer to Section 17.6 for details on reporting Unanticipated Problems.

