#### **17.5. Investigator Reporting: Notifying Bristol-Myers Squibb**

All Serious Adverse Events (SAEs) that occur following the subject's written consent to participate in the study through 30 days of discontinuation of dosing must be reported to BMS Worldwide Safety, whether related or not related to study drug. If applicable, SAEs must be collected that relate to any later protocol-specified procedure (e.g., a follow-up skin biopsy).

Follow-up safety evaluations will occur 30 days ( $\pm$  3 days) after last dose of study drug or until resolution of any drug-related toxicity. Assessment may be collected via telephone if the patient elects to come off study and is no longer coming to clinic.

- Following the subject's written consent to participate in the study, all SAEs, whether related or not related to study drug, are collected, including those thought to be associated with protocol-specified procedures. The investigator should report any SAE occurring after these aforementioned time periods, which is believed to be related to study drug or protocol-specified procedure.
- An SAE report should be completed for any event where doubt exists regarding its seriousness.
- If the investigator believes that an SAE is not related to study drug, but is potentially related to the conditions of the study (such as withdrawal of previous therapy or a complication of a study procedure), the relationship should be specified in the narrative section of the SAE Report Form.

Investigators MUST report within 1 business day upon becoming aware, to the sponsor ANY Serious Adverse Events, whether or not they are considered related to the investigational agent(s)/intervention.

The investigator must inform Bristol-Myer Squibb (using MedWatch Form 3500A) of any SAE within 24 hours of being aware of the event. The MedWatch Form 3500A can be accessed at: <http://www.accessdata.fda.gov/scripts/medwatch/> (the website will instruct you where to send the SAE forms). The BMS protocol ID number must be included on whatever form is submitted by the Sponsor/Investigator.

The initial report must be as complete as possible, including an assessment of the causal relationship between the event and the investigational product(s), if available. Information not available at the time of the initial report (e.g., an end date for the adverse event or laboratory values

Roswell Park Protocol No.: I 47217

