### **19.8. Monitoring of Chronic Toxicities**

Upon completion of the DLT assessment period, patients will be monitored for chronic toxicities utilizing the same DLT/ AE criteria used during the DLT assessment period (see **Section 10.3**).

This monitoring will be done continuously using Bayesian methods. If the posterior probability is 0.80 or greater than 25% or more of treated subjects experience a chronic toxicity, the study will be suspended pending review. This posterior probability will be calculated from the study's accumulating data and a weakly informative prior distribution. If  $\pi$  denotes a random variable representing the proportion of subjects who will experience a chronic toxicity, we assume  $\pi$  has a beta distribution with parameters  $a = 1$  and  $b = 2$ .

Selected values of the posterior distribution  $PP(\pi \geq .25 | \text{chronic toxicities and prior})$  are shown in the table below. Also shown are the binomial probabilities of suspending the study for observed count of chronic toxicities. Note that the study-suspension rules using the Bayesian analysis do not correspond to traditional values of statistical significance, such as 0.05 or 0.10, because our purpose is not to demonstrate unexpected harm, but rather to ensure subject safety.

**Number of Subjects Observed to Have Treatment-Related Chronic Toxicities and Corresponding Posterior and Binomial Probabilities Needed to Suspend the Study**

Subjects	Treatment-Related Chronic Toxicities	$PP(\pi > 25\%)^*$	$Pr(X \geq r   p = .25)$
2	2	.949	.063
3	2	.896	.156
4	2	.831	.262
5	3	.929	.104
6	3	.886	.169
7	3	.834	.244
8	4	.921	.114
9	4	.885	.166
10	4	.842	.224
11	5	.920	.115
12	5	.888	.158
13	5	.852	.206
14	5	.810	.258
15	6	.893	.148
16	6	.861	.190
17	6	.825	.235
18	7	.898	.139
19	7	.870	.175

\* $\pi$  is the chronic toxicity rate. The minimum acceptable upper bound of treatment-related chronic toxicities is 25%.  $PP(\pi > 25\%)$  is the posterior probability that the chronic toxicity rate exceeds this 25% upper bound. This posterior probability of a chronic toxicity is calculated from the prior distribution, the number of subjects treated and the observed number of treatment-related chronic toxicities.

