The table above presents the minimum number of subjects experiencing treatment-related chronic toxicities that would dictate suspension of the trial in accordance with the stopping rule. If a study is suspended for safety concerns, the research team will meet to discuss study termination or possible adjustments to the treatment combination.

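### The protocol states no automatic hold on enrolment after a single treatment-related death: 1 affected of 6 passes the lead-in whatever the grade, and every tabulated row of 19.8 needs at least 2 events

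*Combined protocol and SAP*

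**What the plan says.** **Lead-in (10.2, 19.3).** After six patients have completed a cycle, "the study will be suspended and evaluated for the safety/tolerability of the regimen". The trial then enrols 13 more "If 0 or 1 patient out of 6 has experienced a drug related toxicity requiring treatment delay or suspension". Neither section conditions this on grade or outcome. During the lead-in, data are "discussed and monitored by The Early Phase Clinical Trials committee, which meets on a regular basis per the Roswell Park Data Safety Monitoring Plan".

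**DLT definition (10.3).** Related Grade 5 events are listed together with Grade 4. The stated consequence of a DLT is for the patient: "Should they occur, individual participants will be taken off study and no further injections will be given". Nothing is said there about accrual.

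**Continuous monitoring (19.8).** Once the DLT period is over, the 10.3 criteria are monitored with a Beta(1, 2) prior. The study is suspended pending review under this condition: "If the posterior probability is 0.80 or greater than 25% or more of treated subjects experience a chronic toxicity". The accompanying table "presents the minimum number of subjects experiencing treatment-related chronic toxicities that would dictate suspension of the trial". It runs from 2 of 2 to 7 of 19.

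**Other safeguards.**
- 17.5: "Investigators MUST report within 1 business day upon becoming aware, to the sponsor ANY Serious Adverse Events".
- 17.4.6: "SAEs that are unexpected and possibly, probably or definitely related must be reported as an Unanticipated Problem". Under 17.7.1 this goes through the QA office to the IRB.
- 17.8: a 7-day FDA report for unexpected, related fatal events when Roswell Park holds the IND.
- 18.4: Roswell Park may terminate at once for safety.
- 20: the DSMC reviews Phase II studies semi-annually and may recommend suspension.

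Section 19.7 plans no explicit interim analysis.

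**The concern.** The study-level rules count patients with an event and do not weigh how grave the event is. A related death therefore moves each rule by exactly as much as any other countable toxicity. Section 13 says abatacept has not been combined with standard chemotherapy before, that only one myeloma patient had received it, and that all three drugs are immunosuppressive. After a first related death in this setting, whether the next patient starts before a study-level decision is left to discretion. The patients concerned are those in the remaining lead-in places, and those who enrol after the lead-in and before the next scheduled review.

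**Working it through.** **Inputs from the documents.** Lead-in of 6, passing with 0 or 1 affected, then 13 more (10.2, 19.3). Prior Beta(1, 2), rate limit 25%, threshold 0.80 (19.8). 19 patients over up to 4 years (4, 7). Semi-annual DSMC review (20).

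**Assumptions.** Even accrual, a 4-week out-of-cycle review, and a qualifying-death rate q of 1%, 2% or 5%. The documents give no such rate.

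**1. Reproduce the 19.8 table.** After r events in n patients the posterior is P(Beta(1+r, 2+n−r) > 0.25). The smallest r that reaches 0.80 for n = 2 to 19 is 2, 2, 2, 3, 3, 3, 4, 4, 4, 5, 5, 5, 5, 6, 6, 6, 7, 7. This matches all 18 rows. The posterior values agree to within 0.001 (for example 0.922 against the printed .921 at 4 of 8).

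**2. Put one event into the same rule.** With r = 1 the posterior equals 0.75^(n+2) + (n+2) × 0.25 × 0.75^(n+1).

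| n | Posterior after 1 event | Reaches 0.80? |
|---|---|---|
| 1 (not tabulated) | 0.422 + 0.422 = 0.844 | yes |
| 2 | 0.316 + 0.422 = 0.738 | no |
| 6 | 0.100 + 0.267 = 0.367 | no |
| 19 | 0.002 + 0.017 = 0.019 | no |

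One event never suspends at a tabulated n. At 1 of 1 the prose rule would suspend, but only for an event after the Cycle 1 DLT period, because that is when 19.8 begins.

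**3. Apply the lead-in rule.** Count a death as one affected patient of the six. 1 of 6 is within the pass range, so the stated next step is 13 more patients.

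**4. Exposure before a scheduled review.**
- Accrual is 19/48 = 0.396 patients per month.
- A full DSMC interval is 6 × 0.396 = 2.4 patients. A death at a random time in the interval waits half of it on average, which is 1.2 patients. If accrual took only 2 years, both figures would double (4.8 and 2.4).
- In the lead-in, the sixth patient enrols about 5/0.396 = 12.6 months after the first. A Cycle 1 death in the first patient, treated as outside 19.8, leaves up to 5 more who could start before the scheduled evaluation. If the first patient dies later, after the second has started, 19.8 is again not met (0.738 or lower). The same 5 later patients are then concerned, at most 4 of them still to start. A death after Cycle 1 but before the second patient starts is 1 of 1 and would suspend. The second patient is expected about 1/0.396 = 2.5 months after the first.

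**5. How often a hold would be used.** P(at least one qualifying death in 19) = 1 − (1 − q)^19.
- q = 1%: 1 − 0.99^19 = 0.174
- q = 2%: 1 − 0.98^19 = 0.319
- q = 5%: 1 − 0.95^19 = 0.623

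These are upper bounds on the chance of a pause, since a death after the 19th enrolment leaves nothing to pause. A 4-week review (about 0.92 months) delays 0.92 × 0.396, or about 0.4 enrolments.

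**The case against.** The strongest reply is that nothing here is an error. The table is correct, the rules do not contradict each other, and a related death would not go unnoticed. It reaches the sponsor within one business day, the Early Phase committee watches the lead-in, the study is suspended after six patients whatever has happened, and termination is available at once. The monitoring plan cited in 10.2 may already contain a rule for deaths, and the reader cannot check that. At a death rate of 1–2% the situation usually does not arise.

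Most of this stands, and it limits the point to an optional improvement. What it does not supply is an obligation: each of these provisions informs someone, is scheduled in advance, or permits action. The Unanticipated Problem and 7-day FDA routes also require the event to be unexpected. Section 13 names infection as an added risk and 13.1 lists serious infections, so a fatal infection could be judged expected.

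A reader might infer more than the text supports, in three ways.
- That the trial would have to continue after a death. It would not, because discretionary suspension or termination is always open.
- That up to 5 further patients would always follow a death in the first. This ignores the 1 of 1 case and holds only for the timings in step 4.
- That one could state the probability of a death passing through the count rules. The documents do not allow this. The lead-in counts drug-related toxicity requiring delay or suspension, 19.8 counts 10.3 events after Cycle 1, and no rate is given for either.

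**Conclusion.** The point holds as a statement about the protocol text: no passage automatically holds enrolment after one treatment-related death. The lead-in passes at 1 of 6 regardless of grade, 10.3 acts only on the patient, and 19.8 needs at least 2 events in every tabulated row. The practical size is modest. About 1.2 patients on average, and 2.4 at most, would enrol before the next DSMC review, given even accrual over 4 years and no discretionary pause. The lead-in figure assumes that the patient who died is counted among the six. Section 10.2 also describes that group as patients who completed Cycle 1 without a DLT, so its literal wording leaves this unclear. The conclusion does not depend on how that is resolved. It should be withdrawn if the institutional Data Safety Monitoring Plan already imposes such a hold.

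**What to change.** Add one sentence to 10.2, 19.3 and 19.8: any death judged at least possibly related to the regimen, in any cycle, suspends new enrolment until the existing committee has reviewed it out of cycle and recommended continuation. That committee is the Early Phase Clinical Trials committee during the lead-in and the DSMC afterwards. The count rules stay as they are. If the institutional plan already provides this, citing it would be enough.

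The cost is an occasional short pause, with the probabilities in step 5 as upper bounds and about 0.4 delayed enrolments per review. The sample size and the 9-of-19 efficacy rule are unaffected. A narrower trigger (probably or definitely related, as in 10.3) would pause less often, but could miss infection deaths that can only be called possibly related.
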